1. PROTOCOL SYNOPSIS

Rationale

Raxibacumab was approved for the treatment of inhalation anthrax by the United States (US) Food and Drug Administration (FDA) on December 14, 2012 under the Animal Efficacy Rule per the U.S. Code of Federal Regulations (CFR) (21 CFR § 314.610).

Raxibacumab is a fully human monoclonal IgG₁λ antibody (Ab) which binds the protective antigen (PA) component of the tripartite anthrax toxin, thus blocking the deleterious effects of lethal toxin and edema toxin. Raxibacumab may be administered for prophylaxis of inhalation anthrax when alternative therapies are not available or are not appropriate. Anthrax Vaccine Adsorbed (AVA, BioThrax) which is mainly composed of adsorbed PA, may also be administered as part of a prophylaxis regimen. Published results indicate that a polyclonal anti-PA antitoxin administered to rabbits with AVA resulted in essentially complete abrogation of the immune response to AVA [Malkevich, 2013]. Since the primary antigen in AVA is PA, it is possible that concurrent administration of AVA and raxibacumab would result in raxibacumab binding the PA from AVA, leading to a reduced immune response to the vaccine and decreased anti-PA Ab concentrations and toxin neutralizing activity (TNA) titers. This study, as a post-marketing commitment to the FDA, is designed to detect the effect of raxibacumab on AVA immunogenicity in a healthy volunteer population.

Objective(s)/Endpoint(s)

Objectives	Endpoints
Primary	

 To compare the immunogenicity of AVA at 4 weeks after the first AVA dose, when AVA is administered alone or concomitantly with raxibacumab. 	
 Ratio of geometric mean concentrations (GMC) of anti-PA Ab at 4 weeks after the first AVA dose (prior to the third AVA dose), between the AVA alone and the AVA with raxibacumab treatment groups.
Secondary	

 To compare the immunogenicity of AVA at Weeks 8 and 26 after the first AVA dose, when AVA is administered alone or concomitantly with raxibacumab. To estimate and compare seroconversion, defined as a ≥ 4-fold increase in TNA titer from baseline, at Weeks 4, 8 and 26 after the first AVA dose, when AVA is administered alone or concomitantly with raxibacumab. To describe the safety of AVA when co-administered with raxibacumab versus AVA alone. 	
 Ratio of GMC of anti-PA Ab at Weeks 8 and 26 after the first AVA dose, between the AVA alone and the AVA with raxibacumab treatment groups. Percentage of subjects who seroconvert, at Weeks 4, 8 and 26 after the first AVA dose, between the AVA alone and the AVA with raxibacumab treatment groups. Rates of reported adverse events (AE) as well as review of vital signs, urinalysis and clinical laboratory data in the AVA alone and the AVA with raxibacumab treatment groups.

Overall Design

This is a randomized, open-label, parallel group, two arm study in healthy subjects who have not previously been immunized against PA. Although this is an open-label study, measures have been introduced to minimize bias.

Treatment Arms and Duration

Subjects will be randomized into one of the following treatment groups:

- Treatment Group 1 - subjects will be administered subcutaneous (SC) 0.5 mL AVA doses on Days 1, 15, and 29 (0, 2, and 4 weeks),
- Treatment Group 2- subjects will be administered SC 0.5 mL AVA doses on Days 1, 15, and 29 (0, 2, and 4 weeks), with the first AVA dose administered immediately after completion of a single 40 mg/kg intravenous (IV) infusion of raxibacumab. Subjects will be premedicated with diphenhydramine (25-50 mg) up to 1 hour prior to the raxibacumab infusion to reduce the risk of infusion reactions.

Beginning with the screening visit, the total duration of study for each subject may be approximately 28 to 31 weeks. This study duration was selected because it allows for assessment of the durable immune response to AVA.

Type and Number of Subjects

This study will be conducted in healthy adult subjects who have not been previously immunized against PA.

A total of at least 534 subjects (267 analyzable subjects per treatment group) may be enrolled in the study, in 3 cohorts separated by interim analyses. The trial will continue to subsequent cohorts only if the prospective criteria for discontinuing the trial are not met at the interim analysis. If the outcome of this trial shows a large impact on immunogenicity, then the trial will likely be stopped at one of the two interim analyses.

Subjects will be enrolled in the study in up to 3 cohorts separated by 2 interim analyses. The trial will continue to subsequent cohorts only if the prospective criteria for discontinuing the trial are not met at the interim analysis.

- at least 30 subjects will be enrolled in Cohort 1,
- at least an additional 70 subjects will be enrolled in Cohort 2 if the study progresses beyond interim 1.
- and at least an additional 434 subjects will be enrolled in Cohort 3 if the study progresses beyond interim 2.

Analysis

At the final analysis, the non-inferiority test will be based on a comparison of the confidence interval (CI) for the ratio of anti-PA Ab (attributable to AVA) GMCs between the AVA and the AVA + raxibacumab groups at week 4. This analysis will be performed in the per protocol population. If the upper bound of the 90% CI is less than 1.5, non-inferiority will be established. This analysis will be repeated in the subset of the intent-to-treat population with available week 4 results and in the full ITT population with imputed results for those with missing data, as sensitivity analyses.

The GMC ratio and GMCs within each treatment group and corresponding CIs will be calculated by first log transforming all of the data by a log base 10. CIs will be calculated about the mean logs and the difference of the mean logs assuming these values follow a t-distribution. The results will be translated back to the original scale by exponentiating them, again using a base 10. The exponentiating differences of the sample mean logs will be the ratio of the sample geometric means of the untransformed results.

Two interim analyses are scheduled during this study. A two sample t-test for the log transformed data will be performed and used as the basis of determining whether the futility threshold has been crossed at the respective interim analyses. The futility thresholds for the interim analyses will be based on a rho (0.5) Type II error spending function.

As a secondary endpoint, ratios of the anti-PA Ab GMC for each treatment group at Weeks 8 and 26 will be calculated as described above.

TNA geometric mean titers (GMTs) along with 95% CI will be summarized for each treatment group at each timepoint. The percentage of subjects, along with 95% CI, who seroconvert, defined as a >4-fold increase in TNA titer will be summarized, at Weeks 4, 8 and 26 after the first AVA dose for both arms separately.

Clinical safety observations will include AEs, urinalysis, vital sign measurements, and clinical laboratory assessments. Safety data will be tabulated and, where appropriate, analyzed by the use of descriptive statistics. Safety data will be tabulated for the safety population.

2. INTRODUCTION

2.1. Brief Background

Anthrax is a bacterial zoonosis caused by the gram-positive, aerobic, spore-forming *Bacillus anthracis*. Depending on the route of transmission, anthrax presents in different forms: cutaneous, gastrointestinal, injectional and inhalational [Booth, 2010]. Inhalational anthrax is the most severe form of anthrax because of the rapid progression of the disease to hemorrhagic mediastinitis, toxemia, and massive pulmonary edema, and because of the difficulty in establishing the diagnosis quickly [Dixon, 1999]. The incubation period for inhalational anthrax in humans ranges from 1 to 43 days [Meselson, 1994].

Anthrax Vaccine Adsorbed (AVA) is a current United States (U.S.) Food and Drug Administration (FDA)-approved form of anthrax vaccine. The vaccine requires multiple injections over several weeks before immunity is initially established, so it may not be effective in the event of acute exposure to *B. anthracis* [Bartlett, 2002]

Raxibacumab is indicated for the treatment of adult and pediatric patients with inhalation anthrax due to *B. anthracis* in combination with appropriate antibacterial drugs.

Raxibacumab is also indicated for prophylaxis of inhalation anthrax when alternative therapies are not available or are not appropriate [Raxibacumab Package Insert, 2012]. In contrast to the anthrax vaccine, a single intravenous (IV) dose of raxibacumab provides immediate protection. Section 6 of the raxibacumab Investigator's Brochure (IB, 2013, Version 8) provides a summary of the non-clinical data, including efficacy and the safety profile of raxibacumab in human volunteer studies to date.

2.2. Study Rationale

Raxibacumab was approved for the treatment of inhalation anthrax by the FDA on December 14, 2012 under the Animal Efficacy Rule per the U.S. Code of Federal Regulations (CFR) (21 CFR § 314.610). Raxibacumab is a fully human monoclonal IgG₁λ antibody (Ab) which binds the protective antigen (PA) component of the tripartite anthrax toxin, thus blocking the deleterious effects of lethal toxin and edema toxin.

Raxibacumab may be administered for prophylaxis of inhalation anthrax when alternative therapies are not available or are not appropriate. Anthrax Vaccine Adsorbed (AVA, BioThrax) which is mainly composed of adsorbed PA, may also be administered as part of a prophylaxis regimen. Published results indicate that a polyclonal anti-PA antitoxin administered to rabbits with AVA resulted in essentially complete abrogation of the immune response to AVA [Malkevich, 2013]. Since the primary antigen in AVA is PA, it is possible that concurrent administration of AVA and raxibacumab would result in raxibacumab binding the PA from AVA, leading to a reduced immune response to the vaccine and decreased anti-PA Ab concentrations and toxin neutralizing activity (TNA) titers. This study, as a post-marketing commitment to the FDA, is designed to detect the effect of raxibacumab on AVA immunogenicity in a healthy volunteer population.

3. OBJECTIVE(S) AND ENDPOINT(S)

[figure not shown]
Objectives	Endpoints
Primary	

 To compare the immunogenicity of AVA at 4 weeks after the first AVA dose, when AVA is administered alone or concomitantly with raxibacumab. 	
 Ratio of geometric mean concentrations (GMC) of anti-PA Ab at 4 weeks after the first AVA dose (prior to the third AVA dose), between the AVA alone and the AVA with raxibacumab treatment groups.
Secondary	

 To compare the immunogenicity of AVA at Weeks 8 and 26 after the first AVA dose, when AVA is administered alone 	
 Ratio of GMC of anti-PA Ab at Weeks 8 and 26 after the first AVA dose, between the AVA alone and the AVA with

Objectives	Endpoints
or concomitantly with raxibacumab.	raxibacumab treatment groups.

 To estimate and compare seroconversion, defined as a \geq 4-fold increase in toxin neutralizing activity (TNA) titer from baseline, at Weeks 4, 8 and 26 after the first AVA dose, when AVA is administered alone or concomitantly with raxibacumab. 	
 Percentage of subjects who seroconvert, at Weeks 4, 8 and 26 after the first AVA dose, between the AVA alone and the AVA with raxibacumab treatment groups.

 To describe the safety of AVA when co-administered with raxibacumab versus AVA alone. 	
 Rate of reported adverse events (AE) as well as review of vital signs, urinalysis and clinical laboratory data in the AVA alone and the AVA with raxibacumab treatment groups.

4. STUDY DESIGN

4.1. Overall Design

This is a randomized, open-label, parallel-group, two-arm study in healthy adult subjects who have not previously been immunized against PA. The schematic diagram below illustrates the study design:

4.2. Treatment Arms and Duration

Subjects will be randomized into one of the following two treatment groups:

- **Treatment Group 1-** subjects will be administered subcutaneous (SC) 0.5 mL AVA doses on Days 1, 15, and 29 (0, 2, and 4 weeks).
- **Treatment Group 2-** subjects will be administered SC 0.5 mL AVA doses on Days 1, 15, and 29 (0, 2, and 4 weeks), with the first AVA dose administered immediately after completion of a single IV infusion 40 mg/kg raxibacumab dose. Subjects will be premedicated with 25-50 mg of diphenhydramine up to 1 hour prior to the raxibacumab infusion to reduce the risk of infusion reactions.

Subjects will begin the study with a screening visit up to 35 days before the start of study treatment on Day 1. Results of the screening test for the anti-PA Ab levels must be available prior to randomization on Day -1. Study visits will occur at Days -1, 1, 15, 29, 57, and 183 (Week 26). The total study duration for each subject may be approximately 28 to 31 weeks.

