4.3. Type and Number of Subjects

A total of at least 534 subjects (267 analyzable subjects per treatment group) may be enrolled in the study. Enrollment will occur in 3 cohorts separated by interim analyses. The trial will continue to subsequent cohorts only if the prospective criteria for discontinuing the trial are not met at the interim analysis:

- at least thirty subjects will be enrolled in Cohort 1,
- at least an additional 70 subjects will be enrolled in Cohort 2 if the study progresses beyond interim 1.
- and at least an additional 434 subjects will be enrolled in Cohort 3 if the study progresses beyond interim 2.

If a subject prematurely discontinues the study prior to the Day 29 primary endpoint measurement, additional subjects will be randomized to reach the required number of analyzable subjects for a given analysis (please refer to Section 9.3.1 for definition of an analyzable subject). The goal will be to only enroll the minimum number of subjects to reach the target number of analyzable subjects. Although the number of randomized subjects who will not be analyzable is unknown, based on expectations of study withdrawal and data from previous trials with AVA, it is estimated that no more than 620 subjects will be randomized to reach the target of 534 analyzable. The decision to randomize additional subjects will be made without knowledge of the ongoing comparative results; if ongoing comparative results are known to the Sponsor, no additional subjects may be enrolled.

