6.2. Treatment Assignment

Subjects will be assigned to Treatment Group 1 or Treatment Group 2 in accordance with a balanced independent randomization schedule generated prior to the start of the study. A corresponding set of randomization envelopes (one per subject) will be generated. A

randomization envelope for each subject will be opened prior to dosing (on day -1) to reveal the subject's treatment assignment. This process will ensure that study personnel and the volunteers will have no knowledge of the next treatment to be assigned.

Once a randomization number has been assigned to a subject, it will not be re-assigned to another subject. Randomization numbers will be assigned sequentially as subjects become eligible for dosing.

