7.1. Time and Events Table

Table 1 Screening assessments for subjects administered AVA or co-administered raxibacumab and AVA

Screening Assessments	Days -36 to -15 ^a	Notes
Informed consent process	X	
Demographic information	X	
Inclusion/Exclusion criteria	X	
Medical history (includes substance usage and Family history of premature CV disease)	X	
Physical exam including height and weight	X	
Alcohol and Drug Screening	X	
Urinalysis	X	
Vital signs	X	
Hematology and clinical chemistry	X	Refer to Table 4 for specific laboratory tests.
HIV, Hep B and Hep C screen	X	
Review concomitant medications	X	
Serum or urine pregnancy test	X	
AE/SAE assessment	X	Will capture SAEs reported between Screening visit and Day -1.
Toxin Neutralizing Ab (TNA)	X	
Anti-PA Ab	X	

a. The screening window closes at Day -15 to allow all analyses to be completed to confirm subject eligibility.

Table 2 Treatment Group 1: Time and Events for subjects administered AVA

Protocol Activity	Study Visit						Notes
Assessments	Day -1 ^a	Day 1	Day 15 (± 2 days)	Day 29 (± 2 days)	Day 57 (± 2 days)	Day 183 (± 4 days)	
Inpatient visit	←X→						
Outpatient visit				←-----X-----→			
Urinalysis					X		
Admit to unit	X						
Randomization	X						
Discharge from unit		X					The subject will be discharged from the unit after all assessments are completed.
Vital signs	X	X		X	X	X	
Hematology and clinical chemistry	X			X	X		Refer to Table 4 for specific laboratory tests. On Day 29 the specimen will be collected prior to AVA injection.
Review concomitant medications	X		X	X	X	X	
Serum or urine pregnancy test	X		X	X	X	X	
AVA administration		X	X	X			Each sequential AVA injection will be administered in a different injection site (e.g. alternating arms).
AE/SAE assessment	X	X	X	X	X	X	
Toxin Neutralizing Ab (TNA)		X		X	X	X	On Days 1 and 29 the specimen will be collected prior to AVA injection.
Anti-PA Ab		X		X	X	X	On Days 1 and 29 the specimen will be collected prior to AVA injection.

a. Day -1 is the calendar day preceding Day 1; the designation "Day 0" is not used in this study.

Table 3 Treatment Group 2: Time and Events Table for subjects co-administered raxibacumab and AVA

Protocol Activity Assessments	Study Visit								Notes	
	Day -1 ^a	Day 1				Day 15 (± 2 days)	Day 29 (± 2 days)	Day 57 (± 2 days)	Day 183 (± 4 days)	
		pre-raxi infusion	0 hr	0.5 hr (± 5 min)	2-6 hrs					
Inpatient visit		X								
Outpatient visit						X				
Urinalysis										
Admit to unit	X									
Randomization	X									

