7.2. Screening and Critical Baseline Assessments

After written informed consent is provided, the following data will be collected at the screening visit for all subjects:

- Demographic parameters: year of birth, gender, race, and ethnicity.
- Medical/medication/family history will be assessed as related to the inclusion/exclusion criteria listed in Section 5.
- Physical assessment data including vital signs (temperature, heart rate, systolic and diastolic blood pressure, respiratory rate), height and weight.
- Laboratory assessments (hematology, clinical chemistry)
- Urinalysis
- Alcohol, Drug, HIV, Hepatitis B and Hepatitis C screenings
- A serum or urine pregnancy test on women of childbearing potential
- Blood specimen for anti-PA Ab levels and TNA titers.
- Record of concomitant medications
- Monitoring and reporting of SAEs

The following will be collected as baseline data on Day -1:

- A serum or urine pregnancy test on women of childbearing potential
- Record of concomitant medications
- Vital signs
- Results from clinical chemistry and hematology laboratory evaluations (refer to [Table 4](#) for specific assessments)
- Monitoring and reporting of AEs including SAEs

The following will be collected as baseline data on Day 1 prior to study treatment administration:

- Blood specimen for anti-PA Ab levels and TNA titers

Additionally, for subjects randomized to Treatment Group 2, the following will be collected as baseline data on Day 1 prior to study treatment administration:

- Blood specimen for anti-raxibacumab Ab level

- Blood specimen for serum raxibacumab concentrations

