2.5 Method of Assigning Subjects to Treatment Groups

Subjects will be assigned to Treatment Group 1 or Treatment Group 2 in accordance with a balanced independent randomization schedule generated prior to the start of the study. A corresponding set of randomization envelopes (one per subject) will be generated. A randomization envelope for each subject will be opened just prior to dosing to reveal the subject's treatment assignment. This process will ensure that study personnel and the volunteers will have no knowledge of the next treatment to be assigned.

Once a randomization number has been assigned to a subject, it will not be re-assigned to another subject. Randomization numbers will be assigned sequentially as subjects become eligible for dosing.

To reduce the delay associated with randomizing additional subjects, 34 subjects will be randomized to achieve at least 30 analyzable subjects for the first interim analysis in Cohort 1.

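### The allocation envelope is opened on Day -1, and nothing requires that day's repeat eligibility-related checks to be reviewed first, so eligibility can be reversed with the arm known

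*Protocol*

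**What the plan says.** **Before randomization.** Protocol Table 1 places the inclusion/exclusion review and all screening tests on Days -36 to -15. Its footnote gives the reason: "The screening window closes at Day -15 to allow all analyses to be completed to confirm subject eligibility". Protocol 4.2 adds that "Results of the screening test for the anti-PA Ab levels must be available prior to randomization on Day -1". Protocol 6.2 ties the assignment of numbers to the subject having become eligible for dosing.

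**Opening the envelope.** Protocol 6.2 states that a "randomization envelope for each subject will be opened prior to dosing (on day -1) to reveal the subject's treatment assignment". Protocol Tables 2 and 3 also put randomization on Day -1. SAP 2.5 reads differently: "A randomization envelope for each subject will be opened just prior to dosing to reveal the subject's treatment assignment". It names no day, and SAP Tables 2.2 and 2.3 keep randomization on Day -1.

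**Same-day assessments.** Protocol 7.2 introduces a list with "The following will be collected as baseline data on Day -1". The list covers the pregnancy test, concomitant medications, vital signs, chemistry and hematology, and adverse events. No order relative to the envelope is given.

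**What happens to a subject lost before dosing.** The primary analysis uses the per-protocol population, which requires the Day 1 and Day 15 vaccine doses, raxibacumab if assigned, and a Week 4 result (Protocol 9.3.1, SAP 4.2.3). For subjects who discontinue before the Day 29 measurement, Protocol 4.3 says "additional subjects will be randomized to reach the required number of analyzable subjects for a given analysis".

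**The concern.** Some of what is repeated on Day -1 bears on entry criteria in Protocol 5.2: pregnancy, ALT/bilirubin (no visit is named for that criterion) and the medication washout that runs up to the first dose. Once the envelope is open, site staff and subject know the arm (Protocol 6.3), and dosing is not until the next day. Any Day -1 result or medication finding reviewed in that interval is judged with the arm known.

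The arms differ visibly. One faces premedication and an infusion of about 2 hours 15 minutes; the other has an injection only. Both the investigator's decision to remove a subject and the subject's own willingness to continue could therefore depend on the arm. A subject lost at this point is absent from the primary analysis and also from the Protocol 9.4.1 sensitivity analysis of ITT subjects with available Week 4 results. If such losses differ by arm and are related to response, the primary comparison is no longer fully protected by randomization.

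**Working it through.** **1. Can the Day -1 repeats change eligibility?** There is no Day 0, so the last screening day, Day -15, is 15 days before Day 1. The washout in exclusion criterion 19 is 7 days, 14 days for potential enzyme inducers, or 5 half-lives if longer, counted back from the first dose. Both the 7-day and the 14-day periods begin after Day -15, so screening cannot confirm either. The repeat pregnancy test can likewise show something screening did not. Protocol section 5 allows no deviation from the entry criteria, and Protocol 5.4 lists protocol deviation, investigator discretion and pregnancy among the withdrawal criteria. An adverse finding after opening therefore leads to a removal decision made with the arm known.

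**2. Is the order fixed anywhere?** The Table 1 footnote covers the screening analyses, not the Day -1 repeats. The eligible-for-dosing wording in Protocol 6.2 does not mention them. Protocol Tables 2 and 3 and Protocol 7.2 give the same day without a sequence. SAP 2.5 would leave more time for review, but its own tables do not follow it.

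**3. The plan's own figures.** Inputs are SD 0.75 (log10), 267 per arm, margin 1.5 and one-sided 5% (Protocol 9.2.1), with boundaries 1.0274, 0.4437 and -1.645 at 30, 100 and 534 subjects (Protocol 9.3.2).
- SE = 0.75 × √(4/534) = 0.0649.
- Largest successful observed ratio = 10^(0.1761 − 1.645 × 0.0649) = 10^0.0693 = 1.173, as stated.
- Power at a true ratio of 1, from the three-look multivariate normal probability, is 79.99% (stated: 80%).

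The time at which the envelope is opened enters none of these figures.

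**4. Illustration of size.** The following inputs are assumptions. A fraction f of the combination arm is removed before dosing, and those removed would have responded d SDs below that arm's mean. Replacement restores 267 analyzable subjects, so the number removed is 267 × f/(1 − f), about 5 at f = 0.02 and 14 at f = 0.05.

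The mean of those remaining rises by f/(1 − f) × d × 0.75 on the log10 scale, and the GMC ratio (AVA over combination) falls by 10 to that power. One-sided error at a true ratio of 1.5, ignoring the futility looks, is Φ(−1.645 + shift/0.0649).

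| f | d | Shift (log10) | Factor on ratio | One-sided error |
|---|---|---|---|---|
| 0.02 | 0.25 | 0.0038 | 1.009 | 5.6% |
| 0.02 | 0.5 | 0.0077 | 1.018 | 6.3% |
| 0.05 | 0.25 | 0.0099 | 1.023 | 6.8% |
| 0.05 | 0.5 | 0.0197 | 1.046 | 9.0% |

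**5. What the documents do not supply.** The allowance of 620 − 534 = 86 subjects (86/620 = 13.9%) covers everyone not analyzable, for any reason, up to the Week 4 assessment. It is not a pre-dose loss rate, and none is given.

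**The case against.** The strongest reply is that eligibility is settled before Day -1. Table 1 holds the full eligibility review and closes early so that results are in. Numbers go only to subjects eligible for dosing, and the Day -1 items are called baseline data. This stands against a reading that a reader might take from Protocol 4.2 alone, that the anti-PA result is the only thing required before randomization and that eligibility is first decided with the arm known. The documents do not support that reading. Nor do they suggest failed allocation concealment: there is one envelope per subject and the next assignment is unknown. The reply does not cover a reversal prompted by the Day -1 repeats.

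Other parts of the reply also hold:

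- Criterion 19 needs the sponsor's opinion as well as the investigator's, and the sponsor team, apart from laboratory personnel, is blinded.
- SAP 2.5 names no day, so it is a looser wording to be reconciled with the tables, not a rule for Day 1 opening.
- Withdrawals are reported by arm and reason (Protocol 9.4.2.3, SAP 4.5). The ITT population keeps every randomized subject, with two imputations that work against non-inferiority (Protocol 9.4.1, SAP 4.11). These would help expose a differential loss, but neither corrects the primary estimate, and no table separates losses before the first dose.
- The illustration assumes the loss rate, the response deficit and its direction. Nothing in the documents links a Day -1 finding, or reluctance about an infusion, to a weaker antibody response.

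A reader might also infer that pre-dose losses would by themselves overturn the second imputed ITT analysis. The documents give neither a pre-dose loss rate nor the distance of the quantitation limit from the mean. That analysis is deliberately extreme and moves against non-inferiority, so it says little about when to open the envelope.

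**Conclusion.** The concern holds as a gap in sequencing. The protocol reveals the arm the day before dosing, on the day of repeat checks that can change eligibility, and does not require those checks to be reviewed first. Its wording of the opening time also differs from SAP 2.5. With an open-label design, a per-protocol primary analysis and replacement of lost subjects, arm-aware losses before dosing are possible and would be missing from the primary result.

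The size is unknown. Under the assumed 2-5% removal from the combination arm and a 0.25-0.5 SD deficit, the ratio moves by a factor of 1.009-1.046 towards non-inferiority, and one-sided error at the margin rises from 5% to 5.6-9.0% with the futility looks ignored. Losses from the AVA arm, or of better responders from the combination arm, would change or reverse the effect. The imputed ITT analyses and the reporting of disposition by arm limit the risk but do not remove it. This is a worthwhile, inexpensive improvement; it does not show that the design fails.

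**What to change.** - In Protocol 4.2, 6.2 and Tables 2 and 3, and in SAP 2.5 and Tables 2.2 and 2.3, state one opening time: on Day 1, close to first study treatment, after the Day -1 results have been reviewed and the investigator has signed final eligibility.
- Add to SAP 4.5 a table of every subject randomized but not dosed, by arm and reason. The randomization and treatment-administration listings already planned there hold most of what is needed.

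The change leaves decisions about removing a subject after opening where the protocol puts them. It shortens, but cannot eliminate, the interval in which a subject may decline after learning the arm.

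The cost is wording in both documents and one extra table. No visit is added, because subjects are already admitted on Day -1. The practical downsides are overnight turnaround of the Day -1 samples and a later start to weight-based dose preparation on Day 1.
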